In 2015/16 nationally, uptake in Years 1 and 2 was 53.6%.² Areas that participated in the pilot programme vaccinating primary school children (5-11 years) showed both decreasing uptake with increasing age (from 62.6% in Year 1 to 54.7% in Year 6 in 2015/16) and lower uptake last year than the previous year (57.9% compared with 60.4%). Delivery methods (school, GP or pharmacy) had considerable impact on uptake, with higher uptake in those areas that delivered flu immunisation through schoolsⁱ. Analysis has also shown that lower uptake is associated with deprivation and ethnicity.

The majority of areas offer the immunisation through school-based programmes delivered by providers that are commissioned by the NHS. Parents of eligible children are sent a letter informing them about the vaccination programme and inviting them to return the consent form for their child's vaccination. While uptake in schools is higher than GP or pharmacies, there remains approximately 30% of children for whom consent is neither given nor actively withheld.³

PHE provides template letters that immunisation providers can use. The PHE Behavioural Insights Team has worked with the NHS England and the PHE immunisation team to design the template letter for 2016/17. This letter is informed by behavioural insight theory to encourage parents to return the consent form.

There is evidence from the field of behavioural science to suggest that a low cost intervention, such as the content of an invitation letter or a reminder text message, may be effective in changing behaviour. In a previous trial run by our team, PHE Behavioural Insights Team, a 4% increase in health checks was shown by simplifying invitation letters and adding a tear-off slip where individuals could note the time and

ⁱ (55.6%, 32.9% and 16.1% uptake school, GP and pharmacy delivery respectively)

date of their first appointment, as a memory aid.⁴ Redesigning the invitation letter in combination with primer and reminder text messages increased uptake by 12% compared to the standard letter. Similar effects have been found in other non-health areas, for example, research from the Behavioural Insights Team and the DVLA showed that including an image of a person's car in their car tax collection letter increased tax payments from 40%-49%⁵ and an HMRC trial showed that providing a localised social norm message increased tax returns by 5%.⁶

Here we set out our proposal to test whether behaviourally-informed interventions (i.e. the new template letter and SMS/email reminders) increase uptake of childhood influenza vaccination in schools, through increasing response rate. Such evidence would encourage adoption of the national template letter, which we understand many areas do not currently adopt, provide evidence for the provision of reminders and confirm whether the theory-based changes to the invitation letters have the anticipated impact.

Table 1. Target age groups for national and pilot childhood influenza immunisation programmes, by winter season.

Winter season	National programme ^a	Pilot programme ^a
2013/14	2y and 3y olds (in primary care)	4-11 year olds (reception to school year 6) eligible for vaccination in 7 geographically discrete areas.
2014/15	2-4 years of age (in primary care)	Both primary school aged children (5-11y) and secondary school aged children, 11-13y (school years 7 and 8 age) eligible for vaccination in 14 pilot areas (including pilot areas that participated in 2013/14)
2015/16	2-4 years of age (in primary care) and school years one and two (5y and 6y at 31st August)	6 pilot areas that had piloted the school based programme since 2013 to 2014 continued to offer the vaccine to all primary school age children aged 5-11 years (school years 1 to 6 age).
2016/17	2-4 years of age (in primary care) and School years 1, 2 and 3 (5, 6 and 7y at 31st August)	As in 2015/16 primary school children in years 1 to 6 in former school pilot areas will continue to be offered the vaccine.

^a Ages refer to age on 31st August/1st September of the year

2. Aims and hypothesis

The aim of this study is to investigate whether behavioural insight-informed changes to the invitation process can improve uptake of childhood flu immunisation. Our specific hypotheses are:

[figure not shown]
1. Changes to the invitation letter will increase return of consent forms and thereby increase uptake of childhood flu vaccine through schools.
2. Reminders to return the consent form will increase return of consent forms and thereby increase uptake of childhood flu vaccine through schools

3. Trial design

3.1. Design overview

This is a 2x2 factorial design, open-label, randomised (at school level) trial of invitation letters and SMS/email reminders for childhood flu immunisation (Figure 1).

Figure 1. Randomisation and trial arms

3.2. Primary and Secondary outcomes

The primary outcome for this study is the proportion of children in school years 1-3 who receive influenza immunisation as part of the national childhood immunisation programme.

We will also look at a number of secondary outcomes to determine the effect of the interventions on influenza immunisation in different age groups and on consent-giving. The secondary outcomes are:

- 1) Proportion of children who receive influenza immunisation
 - a) in school years 4-6ⁱⁱ
 - b) in Receptionⁱⁱⁱ
 - c) in each individual year group
- 2) Proportion of children for who consent is neither given nor withheld (i.e. non-responders)
 - a) in school years 1-3
 - b) in school years 4-6
 - c) in each individual year group

3.3. Intervention and control

There are four arms to this 2x2 study:

1. New template invitation letter and SMS/email reminder
2. New template invitation letter and no reminder
3. Last year's invitation (control) letter and SMS/email reminder
4. Last year's invitation (control) letter and no reminder

Parents at schools randomised to one of the new template letter intervention arms will receive the behavioural-insight informed invitation letter (Appendix 1), with minimal local adjustments. The behavioural-insight framing for this letter are summarised in Parents at schools randomised to one of the control letter arms will receive the letter used by the immunisation provider last year (with necessary updates). These letters vary from area to area and examples are given in Appendix 2.

Schools randomised to one of the reminder SMS/email arms will be asked to send a reminder message to parents through their usual email/SMS system (e.g. parentmail). Schools will be asked to send a specific message and for this to be sent at a specified time (

ⁱⁱ Children in School Years 4-6 (age 8-11y) are included in the immunisation programme in pilot areas including Leicestershire and Lincolnshire Area Team and Essex Area Team

ⁱⁱⁱ Reception children (age 4-5y) are being offered immunisation through schools in Essex Area Team.

Table 3). These messages are informed by behavioural insights and are action-orientated with a focus on scarcity in both message (*ensure your child doesn't miss out* and *There will be only one vaccination session at the school*). The email message (with more space) includes other behavioural science informed messages used in the invitation letter. Providers will be given a Standard Operating Procedure detailing how this request to schools is to be made and monitored.

Table 2.

Parents at schools randomised to one of the control letter arms will receive the letter used by the immunisation provider last year (with necessary updates). These letters vary from area to area and examples are given in Appendix 2.

Schools randomised to one of the reminder SMS/email arms will be asked to send a reminder message to parents through their usual email/SMS system (e.g. parentmail). Schools will be asked to send a specific message and for this to be sent at a specified time (

Table 3). These messages are informed by behavioural insights and are action-orientated with a focus on scarcity in both message (*ensure your child doesn't miss out* and *There will be only one vaccination session at the school*). The email message (with more space) includes other behavioural science informed messages used in the invitation letter. Providers will be given a Standard Operating Procedure detailing how this request to schools is to be made and monitored.

Table 2. Behavioural insights informed changes to the flu invitation letter and rationale.

Formatting and phrasing used in new template invitation letter	Behavioural rationale
Formatting	
Reduced in length and made simpler.	Reduces the cognitive effort required to process the information and identify the action required.
We have formatted text to highlight the key points of note/ actions required.	Reduces cognitive effort to identify action required.
Provider letterhead plus NHS logo	NHS is a trusted brand when it comes to medical/ health issues.
Phrasing	
Your child's annual flu vaccination is now due	Salience of message
This vaccination programme is in place to help protect your child against flu.	Gain-framed message for prevention
Flu can be an unpleasant illness and sometimes causes serious complications.	Loss framed message
Please complete the enclosed consent form (one for each child) and return to the school [by/ within] [INSERT DATE or TIME FRAME]	Action orientated
The vaccination is free ...	There is anecdotal evidence that parents do not realise it is free or annual. Note: the evidence on use of 'free' is mixed as this can be deemed as less valuable, particularly by some cultures
... and will be given by a quick and simple spray up the nose	Addresses parental concerns of what the vaccination entails
Last year, most children offered the vaccine in schools had the immunisation.	Social norms

Table 3. Proposed text for SMS and email reminder message

Reminder format	Message	Timing
SMS (160 characters limit)	Thank you for returning your child's flu vaccine consent form. If you have not, please return it by xxxxxx to ensure your child doesn't miss out.	Message to be sent two days ahead of deadline for returning forms
Email	
Subject: Flu vaccine consent form due xx/xx/xx: make sure your child doesn't miss out
 
Dear Parent/Guardian,
 
Please return your child's flu vaccine consent form by [insert day and date] to make sure your child doesn't miss out. Thank you to those parents who have already done so.
 
There will be only one vaccination session at the school. Last year, most children offered the vaccine in schools had the immunisation.
 
[The consent form is attached for use if you have lost the letter]^a
 
If you decide you do not want to vaccinate your child against flu, please return the consent form giving the reason. This will help us plan and improve the service
 
Yours sincerely,
 
SIGNED BY PROVIDER
	Message to be sent two days ahead of deadline for returning forms

^aThis sentence will only be included if feasible to include the original letter as an attachment

3.4. Setting

This trial will be conducted in state schools in participating areas in England. The trial will be implemented by the immunisation providers for the areas and schools themselves will not be aware that they are taking part in a research study.

3.5. Trial Sites

We are working with providers of childhood flu school vaccination in Wessex, Leicester and Essex NHS England Area Teams. We will randomise schools in each of the trial local authority to one of the four trial arms. Details of the areas and providers which we are working with are given in Table 4.

Table 4. Number of schools by area, provider and target cohort.

Local Area Team	Provider	Local authority	Years in prog	Number of schools				
				Total*	Infant	Junior	Primary	Special
Leicester	Leicestershire Partnership NHS Trust	Leicester	Y1-Y6	91	9	9	66	7
		Rutland	Y1-Y6	19	0	0	17	2
		Leicestershire	Y1-Y6	241	6	6	214	10
Essex	South Essex Partnership University NHS FT	Essex	R-Y6	473	51	48	356	16
		Southend on Sea	R-Y6	37	5	5	25	2
		Thurrock	R-Y6	41	0	0	40	1
Wessex	Southern Healthcare Partnership NHS Trust	Hampshire	Y1-Y3	454	117	104	207	26
	Solent NHS Trust	Portsmouth	Y1-Y3	53	16	12	23	2
		Southampton	Y1-Y3	59	10	8	37	4
	Dorset Healthcare Uni Trust	Dorset	Y1-Y3	150	4	4	124	8
		Poole	Y1-Y3	34	8	6	16	3
	Boots UK	Bournemouth	Y1-Y3	32	2	3	26	1
	Boots UK	Isle of Wight	Y1-Y3	42	0	0	40	2
Total				1726	228	205	1191	84

*Independent schools are excluded. Data are taken from <https://www.compare-school-performance.service.gov.uk/download-data>

3.6. Recruitment

Three areas and six providers have agreed to take part in this trial. All schools in their areas will be included in the trial. Due to the nature of the trial and research question, this study will not recruit individual children or individual schools.

3.7. Power calculations

Given that all school-based flu immunisation programmes send invitation letters to parents, even a small increase in uptake from changes to the phrasing of the letter will be worthwhile. Furthermore, given that participating areas will be sending letters to all parents of eligible children it is simpler to include all schools within a participating local authority area. Including a number of providers, which cover 13 local authorities, increases the generalisability of our research findings. We are therefore starting from the position of having potentially ~1700 schools to include in the trial. Sample size calculations are not therefore appropriate as we are not sampling from the participating areas, but rather including the full population. We can however explore the potential power of our study.

Although our allocation will be stratified by local-authority, to explore the potential power of the study we have made the crude assumption that all strata are equal (i.e. that there is no variation between local authorities). We therefore used *sampsi*

followed by the *sampclus* commands in Stata to estimate our study power. We determined the number of schools using data on schools by local authority available from Compare school and college performance website^{iv}. We used 2015/16 data provided for Leicester, Leicestershire and Rutland to estimate the average size of each cluster (i.e. average number of children in school years 1-3) (excluding schools with fewer than 20 pupils in years 1-3). The average size of cohort was 110, and we have therefore conservatively used 100 as our estimate. We used an average vaccine uptake of 63.0% (SD 16.2%) in our power calculations.

We do not have a known value for the intra-class correlation (ICC). Shackleton et al⁷ estimated that ICC values for health outcomes in adolescent children ranged from ICCs ranged from 0.01 to 0.21 depending on the outcome being measured and the country. Within Britain, ICC ranged from 0.01 to 0.15 depending on health outcome, with the highest correlation for regular smoking. These health outcomes are not directly comparable with vaccine uptake or primary school age children (for which the behaviour is actually one of the parents) but nonetheless provide an anchor point around which to explore in the absence of more relevant estimates. We used 0.025 as our basic estimate.

We have conducted power calculations that indicate with this number of schools we would have 90% power to detect a 1% absolute increase in uptake, from 63% to 64% in children in years 1-3. The large number of schools available to us (~1700 schools), will enable us to have 90% power to detect an absolute change even if ICC is relatively high (

^{iv} Available at <https://www.compare-school-performance.service.gov.uk/download-data>

Table 5). Furthermore, we will have the power to detect our secondary outcomes e.g. uptake by year group.

It is possible, due to delays getting this project off the ground, that providers areas will need to go ahead with printing their letters before we have the approvals necessary to issue the randomisation. Our power calculations show that despite this we are likely to have sufficient schools to detect, with 90% power an absolute increase of 2% in uptake, with all but the highest estimates of ICC with just one or two providers (e.g South Essex NHS Partnership Trust, who have indicated a slightly later date for printing letters, has 451 schools. Clearly the size of the effect we have the power to detect will also depend on the impact of variation between strata in the trial (which are not accounted for in these power calculations).

Table 5. Power calculations for various scenarios, assuming no variation between strata.

Outcome	Scenario	Absolute % change able to detect	Power	ICC	Number clusters required in each arm	Total number of schools required
Primary outcome	Detecting lowest absolute effect	1%	90%	0.025	187	748
Primary outcome	Estimate of impact of ICC estimates on required minimum sample size	2%	90%	0.025	47	188
		2%	90%	0.05	81	324
		2%	90%	0.15	214	856
		2%	90%	0.25	347	1388
Secondary outcome	Analysis by individual year group (i.e. average size of the cluster 30)	2%	90%	0.025	78	312
		2%	90%	0.05	110	440
		2%	90%	0.15	240	960
		2%	90%	0.25	370	1480

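### The base-case ICC of 0.025 conflicts with the 16.2% SD of uptake in the same section, which implies about 0.10, and the 1-point power row is run only at 0.025

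*Combined protocol and SAP*

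**What the plan says.** All the inputs are in section 3.7 of the combined protocol and SAP. On the ICC it says: "We do not have a known value for the intra-class correlation (ICC"). It cites a published range for adolescent health outcomes (0.01 to 0.15 within Britain), accepts that these are not directly comparable, and settles on a value: "We used 0.025 as our basic estimate".

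The paragraph before gives data that bear on this choice: "We used an average vaccine uptake of 63.0% (SD 16.2%) in our power calculations". On cluster size: "The average size of cohort was 110, and we have therefore conservatively used 100 as our estimate". On strata: "we have made the crude assumption that all strata are equal (i.e. that there is no variation between local authorities").

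The section then claims "90% power to detect a 1% absolute increase in uptake, from 63% to 64% in children in years 1-3". Table 5 supports this with a single 1% row, at ICC 0.025 (187 clusters per arm, 748 schools). The values 0.05, 0.15 and 0.25 appear only in rows for a 2% change. If approvals come late, the plan expects 90% power for "an absolute increase of 2% in uptake, with all but the highest estimates of ICC with just one or two providers", and gives as its example a provider "who have indicated a slightly later date for printing letters, has 451 schools".

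**The concern.** For a binary outcome, mean uptake, the spread of school rates and cluster size together determine the ICC. The section quotes all three, then takes an ICC from a different outcome in a different age group, and shows no check of one against the other. They disagree by a factor of about four.

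The ICC decides whether the 2-point target is safe, and it lowers the power for 1 point further. The plan says that even a small rise would be worthwhile, so a null result is likely to be read against the stated sensitivity. If that sensitivity is overstated, a null result will look more conclusive than it is.

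**Working it through.** **Inputs.** Section 3.7: p = 0.63, SD = 0.162, mean cohort 110 (100 used for power), base ICC 0.025. Table 4: 1,726 schools, so 863 on each side of a factorial main effect. The section states no significance level; two-sided 5% is assumed.

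**1. The plan's own figure.** Table 5 reproduces with the two-means formula, SD 0.16 and a design effect. For 1 point at 90% power, n = 2 × 0.16² × (1.960 + 1.282)² / 0.01² = 5,380 children per arm. Then 5,380 × (1 + 99 × 0.025) / 100 = 186.96, rounded up to 187, as printed. The other eight rows also match. The table therefore enters a school-level SD as if it were a child-level SD. That is a separate variance error, and it is kept apart from the ICC below.

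**2. What the SD measures.** The child-level SD is √(0.63 × 0.37) = √0.2331 = 0.483. A value of 0.162 can only sensibly be the spread of school rates, although the section neither labels it nor gives its source.

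**3. Implied ICC.** The variance of a school rate is p(1−p)[ICC + (1−ICC)/m]. Solving,

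ICC = (SD²/[p(1−p)] − 1/m) / (1 − 1/m) = (0.02624/0.2331 − 1/110) / (1 − 1/110) = **0.104**.

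In reverse, ICC 0.025 gives a school SD of √(0.2331 × (0.025 + 0.975/110)) = 8.9%, not 16.2%.

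**4. How far the unknowns move it.** Smaller schools: 0.098 at m = 60, 0.090 at m = 40, 0.066 at m = 20 (the plan's exclusion limit). If a share s of the variance between schools lies between authorities, SD² becomes SD²(1 − s). At m = 110, s = 25% gives 0.076 and s = 50% gives 0.048. Reaching 0.025 takes s of about 70% at m = 110, or about 60% at m = 50. The shares are assumptions; the document gives none.

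**5. Power with all schools.** Two-proportion normal approximation with pooled null variance, and effective n per side = 863 × 100 / (1 + 99 × ICC).

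| ICC | Effective n per side | Power, 63% to 64% | Power, 63% to 65% | Effect detectable with 90% power |
|---|---|---|---|---|
| 0.025 | 24,835 | 64% | 99.6% | 1.4 points |
| 0.05 | 14,504 | 42% | 94% | 1.8 points |
| 0.10 | 7,917 | 26% | 75% | 2.5 points |
| 0.15 | 5,445 | 19% | 58% | 3.0 points |

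The 2-point target keeps 90% power up to an ICC of about 0.062.

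**6. Check that uses no ICC.** Comparing school rates directly, SE = 16.2 × √(2/863) = 0.78 points. Power is Φ(1/0.78 − 1.96) = 25% for 1 point and Φ(2/0.78 − 1.96) = 73% for 2 points. The detectable effect is 3.24 × 0.78 = 2.5 points. This agrees with the row at ICC 0.10. If half the variance lay between authorities (SD 16.2 × √0.5 = 11.5 points), the figures are 44%, 95% and 1.8 points.

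**7. Fall-back, power for 2 points** (variance correction included).

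| Schools | ICC 0.025 | ICC 0.05 | ICC 0.10 | Highest ICC that keeps 90% |
|---|---|---|---|---|
| 451 (section 3.7) | 66% | 44% | 27% | 0.009 |
| 551 (same provider in Table 4: 473 + 37 + 41) | 75% | 52% | 32% | 0.013 |
| 1,005 (two largest providers: 551 + 454) | 94% | 77% | 52% | 0.032 |

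**The case against.** The strongest reply is that most of the lost power belongs to the variance error. By Table 5's own method, ICC 0.10 needs 147 clusters per arm (588 schools in four arms) for 2 points. For 1 point it needs 587 per arm: 2,348 schools in the four-arm layout, but only 1,174 for a two-group main effect, which 1,726 schools would cover. This is correct. Within that method the ICC alone does not defeat the 2-point claim, and the figures of 75% and 26% appear only once the variance is put right. It is a reason to make the two corrections together. It does not defend 0.025, since correcting the variance and keeping that ICC would still overstate power.

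Second, about 0.10 takes literally a simplification that the plan itself admits is crude. Randomisation is stratified by provider and authority (section 3.8) and the model includes authority (section 3.10), so the within-authority ICC is what matters, and it may be lower. School covariates in the model could lower it further. This stands: 0.10 is firm as the overall ICC, not as the within-authority value. The two unknowns can also act together: a 50% share between authorities combined with an effective school size of 30 would give 0.024. Nothing in the document supports so small an effective size against a mean of 110.

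Third, Table 5 already runs values on either side of 0.10 for 2 points. That is true, but it does so on the understated variance and not at all for 1 point.

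Last, every school is included whatever the calculation shows, so only the stated power changes. That limits the seriousness of the point without removing it.

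**Conclusion.** The concern holds. The section's own mean, SD and cohort size imply an overall ICC of about 0.10, four times the base case, and under the plan's assumption of no differences between authorities that is the value to use. Over an assumed share between authorities of 0 to 50%, the range is about 0.10 to 0.05.

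Over that range, 2 points with all schools has about 75% to 94% power, and the effect detectable with 90% power is about 2.5 to 1.8 points. For 1 point, the fall from 90% to 64% is due to the variance error; the ICC accounts for the further fall to between 42% and 26%. The fall-back claim fails for the single provider even at 0.025 because of the variance correction. For the two largest providers it holds at 0.025 but not at 0.05.

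These figures assume that 16.2% is the spread of school rates, an equal school size of 100 as in the plan, two-sided 5%, and no gain from covariates. All 1,726 schools are counted at that size, although the mean of 110 leaves out schools with fewer than 20 pupils in years 1-3.

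**What to change.** 1. State what the 16.2% measures and which data it comes from.
2. Estimate the within-authority ICC from the 2015/16 school-level data and use it as the base case in place of 0.025.
3. Run the 1% and 2% rows over an ICC of about 0.05 to 0.15, on the binary scale, for the two-group main-effect comparison.
4. Restate the headline power and detectable effect once, together with the Table 5 variance correction, so that the loss is not counted twice.
5. Reconcile the 451 schools in section 3.7 with the 551 in Table 4 for the same provider, then restate the one-or-two-provider fall-back on the same basis.

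The cost is a short calculation and a few extra table rows. The sponsor already used 2015/16 data for cluster size, and section 3.9 says that school-level data reach it routinely. Enrolment, allocation and design do not change; the only downside is a less favourable statement of power.

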3.8. Randomisation

Randomisation will be undertaken by PHE Behavioural Insights Team. An up-to-date list of schools will be obtained from each area (or obtained from PHE and validated by the local team). Schools will be identified by their Unique Reference Number (School URN) to create the allocation list. Randomisation will be stratified by Provider and local authority. It is unlikely that we will know in advance (i.e. at the time of randomisation) which schools have email/SMS systems. (We anticipate this to be fairly common amongst schools.) We will therefore allocate all schools, irrespective of their available system, to one of the four trial arms. Randomisation will be carried out using a randomisation tool (e.g. ralloc or random number generator with schools ranked for allocation by random number order) in Stata, or other appropriate statistical-package to one of the four arms of the trial.

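### Table 5 treats a 16% spread between schools as a child-level SD: schools per comparison group are about 9 times too few, and the claimed 90% power for 1 point is about 64%

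*Combined protocol and SAP*

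**What the plan says.** Section 3.7 gives the inputs: "We used an average vaccine uptake of 63.0% (SD 16.2%) in our power calculations", a cluster size of 100 children in Years 1-3 (30 for a single year group), and for the ICC, "We used 0.025 as our basic estimate". It cites outside values as an anchor: "Within Britain, ICC ranged from 0.01 to 0.15 depending on health outcome". No alpha is stated, nor the unit to which the SD applies.

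Four power statements follow:

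- The headline: "we would have 90% power to detect a 1% absolute increase in uptake, from 63% to 64% in children in years 1-3". The first row of Table 5 puts this at 187 schools per arm, 748 in total.
- The large number of schools "will enable us to have 90% power to detect an absolute change even if ICC is relatively high", with a reference to Table 5, whose 2-point rows run up to ICC 0.25.
- If printing deadlines are missed, the plan expects 90% power for 2 points "with all but the highest estimates of ICC with just one or two providers". South Essex is the example, with 451 schools.
- "Furthermore, we will have the power to detect our secondary outcomes e.g. uptake by year group".

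The primary outcome (section 3.2) is the proportion of children vaccinated, analysed by logistic regression (section 3.10).

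**The concern.** A yes/no outcome with a mean of 63% cannot have an SD of 16% at child level. A figure of that size describes the spread of uptake between schools, which already contains the clustering. Using it as the child-level SD and then applying a design effect gives far too small a variance.

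The plan argues that even a small gain from a letter is worthwhile, so the 1-point claim matters. A null result read against a claimed 90% power could be taken to rule out an effect that the trial had a sizeable chance of missing. The same table supports the statement that one or two providers would be enough.

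**Working it through.** **Inputs.** From section 3.7: uptake 63%, SD 16.2%, m = 100 or 30, ICC 0.025 to 0.25, power 90%. From Table 4: 1,726 schools. Assumed: two-sided alpha 0.05, equal allocation, equal cluster sizes, no variation between strata. In the factorial design each main effect compares half the schools with the other half (863 v 863).

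**1. Reproducing Table 5.** Two means with SD 16:

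n per group = 2 × 16² × (1.96 + 1.2816)² / δ² = 5,380 for 1 point and 1,345 for 2 points.

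Schools = n × [1 + (m − 1) × ICC] / m, rounded up. First row: 5,380 × 3.475 / 100 = 186.96, giving 187. All nine rows match. With SD 16.2 unrounded, the first row is 192 and the others are equally close but not exact. Two-proportion versions give 996 to 1,700 for the first row, and a one-sided comparison of means gives 153.

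**2. Corrected counts.** Child-level SD = √(0.63 × 0.37) = 48.3%, and (48.3/16)² = 9.1. The pooled two-proportion formula without continuity correction gives 48,706 children per group for 63% v 64%, and 12,103 for 63% v 65%. The design effect is unchanged.

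| Effect | m | ICC | Table 5, per group | Corrected, per group |
|---|---|---|---|---|
| 1 point | 100 | 0.025 | 187 | 1,693 |
| 2 points | 100 | 0.025 | 47 | 421 |
| 2 points | 100 | 0.05 | 81 | 721 |
| 2 points | 100 | 0.15 | 214 | 1,919 |
| 2 points | 100 | 0.25 | 347 | 3,117 |
| 2 points | 30 | 0.025 | 78 | 696 |
| 2 points | 30 | 0.05 | 110 | 989 |
| 2 points | 30 | 0.15 | 240 | 2,159 |
| 2 points | 30 | 0.25 | 370 | 3,329 |

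The ratio is 8.9 to 9.05. Table 5 totals multiply by four arms, whereas a main effect needs two groups. The first row therefore needs 2 × 1,693 = 3,386 schools in total: 4.5 times the stated 748 and about twice the 1,726 available.

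**3. Power with all 1,726 schools.** Effective n per group = 863 × 100 / [1 + 99 × ICC]. At ICC 0.025 this is 86,300 / 3.475 = 24,835, against 48,706 needed.

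| ICC | 1 point | 2 points |
|---|---|---|
| 0.01 | 86% | over 99% |
| 0.025 | 64% | 99.6% |
| 0.05 | 42% | 94% |
| 0.10 | 26% | 75% |
| 0.15 | 19% | 58% |
| 0.25 | 13% | 40% |

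Power of 90% requires an ICC of at most about 0.008 for 1 point and 0.062 for 2 points. Table 5 implies that 2 points is safe at 0.25, with 1,388 schools.

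**4. Fallback, 2 points.**

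| Providers | Schools | ICC 0.025 | ICC 0.05 | ICC limit for 90% |
|---|---|---|---|---|
| South Essex, count in text | 451 | 66% | 44% | 0.009 |
| South Essex, Table 4 (473 + 37 + 41) | 551 | 75% | 52% | 0.013 |
| South Essex + Leicestershire (551 + 351) | 902 | 92% | 73% | 0.028 |
| South Essex + Southern (551 + 454) | 1,005 | 94% | 77% | 0.032 |

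**5. Single year groups, 2 points, m = 30, base uptake 63% assumed throughout.**

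- Each of Years 1-3: 95% at ICC 0.025 and 86% at 0.05 with 1,726 schools; 92% and 81% with 1,521 (the 205 junior schools removed).
- Years 4-6: 351 + 551 − 71 infant = 831 schools, 71% at ICC 0.025.
- Reception: 551 − 53 junior = 498 schools, 49% at ICC 0.025 and 72% even at ICC 0.

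**6. SD against ICC.** With pq = 0.2331, a school SD of 16.2% implies ICC = (0.162² − pq/m) / [pq(1 − 1/m)] = 0.104 at m = 100 (0.094 at m = 50). Conversely, ICC 0.025 implies a school SD of √(0.2331 × 3.475 / 100) = 9.0%. If the full 16.2% applied, SE = 16.2 × √(2/863) = 0.78 points, so power would be 25% for 1 point and 73% for 2 points.

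**The case against.** The plan says that it includes every school in the participating areas, that a sample size calculation is therefore not appropriate, and that it is only exploring power under crude assumptions. On that view nothing operational depends on Table 5, and the fallback is driven by print deadlines. This is true of enrolment, allocation and analysis, and it limits the harm. It does not make the stated powers right. The caveat in section 3.7 concerns variation between strata, not variance within schools.

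The mechanism is inferred. The plan states 16.2%, the exact match needs 16%, alpha is assumed, and the unit of the SD is not given (school-by-year cells are possible). That stands as a limit on the explanation. The corrected counts do not depend on it: they use only the plan's uptake, cluster size and ICC, plus the assumed alpha.

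The high-ICC sentence names no effect size, and the fallback is worded as likely. Both statements lean on the 2-point rows of Table 5, however. Two large providers do reach 92 to 94% at ICC 0.025; by 0.05 even the largest pair has 77%, which does not fit a claim covering all but the highest ICCs.

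The ICC of about 0.10 is an upper bound, since "Randomisation will be stratified by Provider and local authority" and stratification may remove part of the spread.

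Finally, crediting all 1,726 schools with 100 children in Years 1-3 is generous. Without the junior schools, power for 1 point falls from 64% to 58%.

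**Conclusion.** The concern holds. Table 5 understates the schools needed per comparison group about 9-fold (4.5-fold in total for a factorial main effect). The headline power is 64%, not 90%, at the plan's own ICC, and it stays below 90% even at 0.01, the bottom of the cited range. These figures assume two-sided alpha 0.05, equal clusters of 100, all 1,726 schools contributing, and no variation between strata. A higher ICC or fewer contributing schools would lower them.

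The trial remains informative for 2 points with all schools up to an ICC of about 0.06. The high-ICC and fallback statements do not hold across the ICC range that Table 5 presents. The year-group statement holds for Years 1-3 at ICC 0.025, but not for Years 4-6 or Reception. This should be corrected before the plan is relied on.

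**What to change.** - Recompute Table 5 from p(1 − p) times the design effect, with totals at the factorial margin, and state alpha.
- Say what the 16.2% SD measures and resolve its conflict with ICC 0.025. Show results over ICC 0.025 to 0.10.
- Replace the 1-point claim with the effect detectable at 90% power with 1,726 schools: about 1.4 points at ICC 0.025, 1.8 at 0.05 and 2.5 at 0.10.
- Restate the high-ICC, fallback and year-group sentences from the new table, with Years 4-6 and Reception shown separately.
- Reconcile the 451 South Essex schools in the text with the 551 in Table 4, because the fallback power depends on the count.

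The cost is one table and about four sentences. No schools are added and the design does not change. The stated power becomes less favourable.
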